# 6. ELIGIBILITY CRITERIA

#### 6.1. INCLUSION CRITERIA

- Adult Patients (≥18 years) affiliated to a social insurance protection regimen.
- Patients with moderate to severe chronic ( $\geq 6$  months) hand eczema with an Investigator global assessment (IGA) of 3 or 4 (out of a scale of 0 to 4).
- Patients intolerant (according to the physician) or resistant to highly potent topical corticosteroids. Inadequate response (resistance) to highly potent topical corticosteroids is defined as a history of failure to achieve and maintain remission or a low disease activity state (comparable to an IGA score of 0 [indicating clear] to 2 [indicating mild]) despite treatment with a daily regimen of highly potent topical corticosteroids applied for 14 days or for the maximum duration recommended for highly potent topical corticosteroids.
- Patients who are able to understand the study procedures including the ability to complete patientoriented questionnaires.
- Patients who are able to apply a stable dose of emollients within 7 days before the baseline visit.
- Patients who agree to sign the written informed consent.

#### **6.2 EXCLUSION CRITERIA**

- Hypersensitivity to dupilumab or to any of its ingredients
- Patients under adult autonomy protection system
- Any other condition (e;g., psoriasis) on the hands that according to the investigator will impair the ability to evaluate treatment effect.
- Treatment with topical corticosteroids or topical calcineurin inhibitors within one week of baseline.
- Treatment with oral immunosuppressants (including cyclosporine, methotrexate, azathioprine, mycophenolate mofetil), alitretinoin or phototherapy within 4 weeks of baseline visit.
- Treatment with an investigational drug within 8 weeks (or 5 half-lives) of baseline.
- Active chronic infection requiring the use of a systemic antibiotic within 2 weeks before study start.
- Known or suspected history of immunosuppression, including history of invasive opportunistic infections (e.g., tuberculosis, histoplasmosis, listeriosis, coccidioidomycosis, pneumocystis, aspergillosis) despite infection resolution; or unusually frequent, recurrent, or prolonged infections, per investigator judgment.
- History of human immunodeficiency virus (HIV) infection or positive HIV serology at screening.
- Positive for hepatitis B surface antigen, hepatitis B core antibody, or hepatitis C antibody at the screening visit.
- Patients with known helminth infections.
- Pregnant or breastfeeding women, or women planning to become pregnant or breastfeed during the study. Women of childbearing potential who are sexually active and unwilling to use an adequate birth control method.

#### 7.1. METHODS OF RECRUITMENT

Patients will be recruited from the outpatient dermatology and allergology clinics of the participating centers. The participating centers are tertiary care referral centers for patients with moderate to severe hand eczema. They have a dedicated dermato-allergology clinic and are able to select 2 to 3 patients who are potential candidates for the study each month.

The regional network of office and hospital based dermatologists from the participating regions will be contacted for organizing patients referral. In addition, the network of occupational physicians in the participating regions will be informed about the study.

# 8. STUDY TREATMENTS/STRATEGIES/PROCEDURES

# 8.1. TREATMENT/STRATEGY/PROCEDURE BEING STUDIED

Dupilumab 300 mg syringe (2 mL) or matching placebo for subcutaneous administration. Two injections	of
300 mg dupilumab or matching placebo will be performed at day 0 followed by one injection of 300 mg	01
matching placebo every 2 weeks until week 14.	

#### 8.2.1. DISTRIBUTION AND MANAGEMENT OF MEDICINAL PRODUCTS

At the start of recruitment, enough kits will be sent to each site (buffer) to allow for initial treatment allocations in case several patients are recruited simultaneously, until the next shipment can arrive.

The Investigator, the hospital pharmacist, or dedicated personnel allowed to store and dispense the IMP (Investigational Medical Product) will be responsible for ensuring that the IMP used in the clinical trial is securely maintained as specified by the Sponsor and in accordance with applicable regulatory requirements. When the opening and the reglementation of the study will be sorted, the different pharmacies will be contacted to store two complete kits (each kit containing 10 syringes) according to the randomization list in order to have the complete treatment for 2 patients.

When a patient is randomized, the pharmacy of the center or the local study team will sent to the center pharmacy a prescription with the scheduled visit date. The pharmacy will deliver the treatment for one month to the patient and an order will be sent to the PCEC of Toulouse to get a subsequent kit for the next patient. This will be sent by Toulouse to the center in the week following the order.

The subsequent dispensations to the clinical trial unit will be organised after the planification of each visit for a patient. This will be traced in the prescription form and the reception of IMP and its administration will be recorded in the tracability logs.

#### 8.2.2. DISPENSING THE MEDICINAL PRODUCT

All IMPs will be dispensed in accordance with the Investigator's prescription and it is the Investigator's responsibility to ensure that an accurate record of IMP issued is maintained.

Any quality issue noticed with the receipt or use of an IMP (deficiency in condition, appearance, pertaining documentation, labeling, expiration date, etc) should be promptly notified to the Sponsor. Some deficiencies may be recorded through a complaint procedure.

A potential defect in the quality of IMP may be subject to initiation of a recall procedure by the Sponsor. In this case, the Investigator will be responsible for promptly addressing any request made by the Sponsor, in order to recall IMP and eliminate potential hazards.

Under no circumstances will the Investigator supply IMP to a third party, allows the IMP to be used other than as directed by this clinical trial protocol, or dispose of IMP in any other manner.

The Investigator or delegate will keep accurate records of the quantities of the IMP dispensed, used and unused by each patient.

Proper recording of treatment kit numbers will be done as required on appropriate electronic case report form (e-CRF) page for accounting purposes.

The Investigator (or designee) tracks treatment accountability/compliance, either by diary, or by counting the number of used and unused treatment kits and syringes and completes the appropriate page of the patient treatment log.

The monitor in charge of the study then checks the data entered on the IMP administration page (in e-CRF) by comparing them with the patient treatment log forms.

Dupilumab and placebo will be administered by subcutaneous injection by a dedicated nurse during dedicated visits. Therefore, compliance will be guaranteed.

#### **8.2.3.STORAGE**

All IMP should be stored in an appropriate, locked room under the responsibility of the Investigator or other authorized persons (eg, pharmacists) in accordance with local regulations, policies, and procedures.

Control of storage conditions, especially control of temperature (eg, refrigerated storage) and information on in-use stability and instructions for handling the Sanofi compound should be managed according to the rules provided by the Sponsor.

Dupilumab and placebo will be stored refrigerated at 2°C to 8°C in the original carton to protect from light.

#### 8.2.4. RETURN AND DESTRUCTION OF UNUSED PRODUCTS

The destruction of all used and unused units provided by SARD will be the responsibility of the Sponsor who will manage the organization and all logistics related to this activity. The destruction of non-shipped and/or expired units remaining at SARD will be the responsibility of SARD who will manage the organization and all logistics related to this activity after obtaining a greenlight from the Sponsor.

The Sponsor is responsible for ensuring that adequate records are maintained regarding the accountability and traceability of the units delivered to investigational sites as required by and in accordance with applicable law, statutes and regulations. The Sponsor is responsible for ensuring that reconciliation is performed for all units delivered to investigational sites.

#### 8.3. BLINDING

#### 8.3.1. Organisation of blinding

Dupilumab and placebo will be provided in identically matching 2 mL pre-filled syringes. To protect the blind, each treatment kit of 2 mL (dupilumab/placebo) glass pre-filled syringes will be prepared such that the treatments (dupilumab and its matching placebo) are identical and indistinguishable and will be labeled with a treatment kit number. The treatment kit number list will be generated by SARD. This list gives the correspondence between the treatment numbers and the treatment arms (dupilumab or placebo). Both the patient and Investigator will be blinded to assigned active drug or placebo for the whole study period.

#### 8.3.2. Unblinding

Investigators may request unblinding for a participant for safety purpose. These requests will be made to the pharmacy unit of the Toulouse Hospital. Each intentional break of the blind should be reported to the sponsor and documented in the patient's CRF.

The PCEC will provide blinding letters to the centers in order to allow for the emergency unblinding if necessary.

The sponsor's vigilance unit will also have the randomization list and the correspondence between the numbers and the content of syringes in case of required unblinding (for potential suspected unexpected serious adverse reaction (SUSAR) regulatory notification).

Treatment allocation will be provided at the end of the study for all subjects after last subject has completed the study, complete cleaning of database and statistical analysis plan validated.

# 9. ASSOCIATED TREATMENTS AND PROCEDURES

#### 9.1. APPROVED ASSOCIATED TREATMENTS/PROCEDURES

Emollients are approved for use in patients during the course of the study. Patients are allowed to take anti-histamines if medically indicated during the study. Patients with comorbid asthma should be on stable treatment. Any change in the dosage of anti-histamines should be captured in the source documents and case report form.

# 9.2. PROHIBITED ASSOCIATED TREATMENTS/PROCEDURES

Some treatments/procedures are prohibited during the study as either they may influence disease outcome or may pose a safety risk for patients.

Treatment with the following concomitant medications is prohibited during the study

- Treatment with immunomodulating biologics
- Treatment with an investigational drug (other than dupilumab)
- Treatment with topical corticosteroids or topical calcineurin inhibitors; such agents should not be administered during the study.
- Treatment with systemic corticosteroids or non-steroidal systemic immunosuppressive drugs (e.g., cyclosporine, methotrexate, mycophenolate-mofetil, azathioprine, etc.), except if critically medically needed to treat concurrent medical conditions (e.g., asthma).

Study drug will be temporary discontinued (5 half-life before and after vaccination) if a treatment with live (attenuated) vaccine is used through week 16

In addition, major surgery procedure and phototherapy (medical device or tanning) are prohibited during the 16-week treatment period.

**Rescue therapy:** if a patient presents with a severe flare of CHE during the course of the study which cannot be managed with emollients and requires intervention, a unique rescue 2-week course of highly potent corticosteroid (betamethasone dipropionate cream) will be administered. The amount of drug used will be recorded. Study treatment will be unchanged.

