INCLUSION CRITERIA	- Adult Patients (≥18 years) affiliated to a social insurance protection regimen Patients with moderate to severe chronic (>6 months) hand eczema with an Investigator global assessment (IGA) of 3 or 4 (out of a scale of 0 to 4) Patients intolerant or resistant to highly potent topical corticosteroids. Inadequate response to highly potent topical corticosteroids is defined as a history of failure to achieve and maintain remission or a low disease activity state (comparable to an IGA score of 0 [indicating clear] to 2 [indicating mild]) despite treatment with a daily regimen of highly potent topical corticosteroids applied for 14 days or for the maximum duration recommended for highly potent topical corticosteroids Patients who are able to understand the study procedures including the ability to complete patient-oriented questionnaires Patients who are able to apply a stable dose of emollients within 7 days before the baseline visit Patients who agree to sign the written informed consent.

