# 4. OBJECTIVES OF THE STUDY

#### 4.1. PRIMARY OBJECTIVE

The primary objective of the study is to demonstrate that dupilumab is more effective than placebo for the treatment of patients with moderate to severe chronic hand eczema (CHE) who are resistant or intolerant to highly potent topical corticosteroids as determined by the evolution at week 16 of the mTLSS since baseline.

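### Patients may enter because they are intolerant to highly potent topical corticosteroids, yet the only rescue named is a drug of that class, with no exception for them

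*Protocol*

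**What the plan says.** Protocol section 6.1 sets the entry criterion as "Patients intolerant (according to the physician) or resistant to highly potent topical corticosteroids". The synopsis has the same two routes: "Patients intolerant or resistant to highly potent topical corticosteroids". Resistance is then defined in some detail, by failure to reach and hold low disease activity on a daily regimen. Intolerance is not defined beyond the physician's opinion. Section 4.1 describes the target population of the primary objective as those "who are resistant or intolerant to highly potent topical corticosteroids".

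The rescue paragraph in section 9.2 applies "if a patient presents with a severe flare of CHE during the course of the study which cannot be managed with emollients and requires intervention". In that case "a unique rescue 2-week course of highly potent corticosteroid (betamethasone dipropionate cream) will be administered". The amount used is recorded and study treatment continues unchanged. The paragraph does not distinguish patients by route of entry and names no other rescue.

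The list above it in section 9.2 includes "Treatment with topical corticosteroids or topical calcineurin inhibitors; such agents should not be administered during the study". It also bars immunomodulating biologics, and systemic corticosteroids and immunosuppressants except for concurrent conditions. Phototherapy is barred during the 16-week treatment period. Section 9.1 permits emollients, and antihistamines if medically indicated. In section 6.2 the hypersensitivity exclusion concerns dupilumab and its ingredients only.

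**The concern.** The protocol uses the same class label in both places. Intolerance to highly potent topical corticosteroids is a sufficient reason to enrol, and a highly potent corticosteroid cream is what the patient is to receive in a severe flare. The rescue wording is directive and applies to any patient.

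The first issue is patient safety: read literally, the rescue provision exposes a patient to the class that the physician judged the patient could not tolerate. The second is uniformity: with intolerance undefined and no instruction for this case, each site has to decide for itself. The third is interpretation of the trial. If dupilumab works as section 3.2 hypothesises, severe flares should be commoner on placebo, so whatever sites do in this situation could fall unevenly between the arms. Use of a forbidden drug is one of the examples in section 13.3 of a major deviation that removes a patient from the Per-Protocol population. A patient who withdraws before Week 16 enters the primary analysis through LOCF (section 13.4).

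**Working it through.** The point rests on reading the passages together and on no figure.

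1. **Who enters.** Sections 2 and 6.1 join intolerant and resistant with an or, so intolerance alone suffices. Section 4.1 confirms that the intolerant group belongs to the population about which the trial is to conclude.

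2. **What happens in a severe flare.** Section 9.2 has a single trigger (severe flare, emollients insufficient, intervention required) and a single response (one course of a highly potent corticosteroid). Since the same section also bars topical corticosteroids during the study, the rescue course has to be read as an exception to that ban. No further exception is written for the intolerant group.

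3. **Does another section close the gap?** Section 6.2 has no exclusion for intolerance to the rescue agent. Section 9.1 leaves emollients and antihistamines available, but the trigger presupposes that emollients have not sufficed, and neither is described as rescue. Nothing in section 11 distinguishes patients by entry route.

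4. **What follows for a site.** For a patient entered as intolerant who meets the trigger, the site either gives a drug of the class named in the entry criterion or departs from section 9.2. Both passages cannot be given full effect at the level at which they are worded, which is the drug class.

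5. **Can it be sized?** The number affected would be

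   affected = 94 × (share entered as intolerant) × (share of those with a qualifying flare) × (share of those unable to use the named cream).

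   Only the 94 is in the protocol. Assuming an intolerant share of 5% to 50%, the first product runs from 94 × 0.05 = 4.7 to 94 × 0.50 = 47. These are ceilings, reached only if every intolerant patient flares and none can use the cream. Since the last two factors are not given, the affected number could lie anywhere from 0 to the ceiling.

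6. **The sample-size allowance is not a yardstick.** The plan's inflation reproduces: 84 / 0.90 = 93.3, rounded up to 94, leaving 94 − 84 = 10 for non-evaluable patients. An intolerant patient who never has a qualifying flare is fully evaluable, so counts of intolerant patients cannot be set against those 10.

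**The case against.** The strongest reply is that this is a missing clarification. Section 6.1 leaves intolerance to the physician and does not tie it to an agent, formulation, duration or type of reaction. A patient intolerant to one product might manage a single limited course of the named cream, and clinical judgement decides whether the trigger is met. That stands in part. A reader might infer that intolerant patients have no usable rescue at all, and the documents do not establish this. They do show a rescue that is inconsistent with the entry criterion at class level, and no rule telling sites how to resolve it.

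Other strong readings also go too far:

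- **That every alternative is banned.** The prohibited list in section 9.2 does not name alitretinoin, which section 6.2 restricts only before baseline, and antihistamines remain allowed. This is an observation about the text, not a suggestion for treatment. Neither is offered as rescue.
- **That sites are forced into a violation or the loss of Week 16 data.** Section 16 excepts emergency situations from strict adherence, and section 11.7 lets a patient who stops treatment remain in follow-up.
- **That reactions to the cream would be booked against the blinded study drug.** Section 12.3 requires a causality assessment for each event and lists concomitant treatment as a possible alternative cause for serious events. Section 9.2 records the amount of rescue used, and section 11.4 records concomitant medication with reason, dates and dose. Attribution to the cream is possible.
- **That the entry reason is not captured.** The eCRF is not shown, and sections 5.2 and 11.4 require eligibility to be checked before randomisation. The protocol text does not ask for the entry reason, but the form may.

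None of this supplies the missing instruction for the intolerant group, and an analysis plan cannot supply it, because eligibility and rescue are fixed in the protocol.

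**Conclusion.** Sections 6.1 (with sections 2 and 4.1) and 9.2 conflict for one of the two entry routes. Followed as written, the rescue provision gives patients entered as intolerant the class whose intolerance justified their entry, unless the site departs from it. This is a patient-safety inconsistency that should be corrected, even though it concerns a subgroup and not every patient.

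Its size is unknown. The protocol gives no intolerant share, no rate of severe flares and no definition of intolerance, so neither the number affected nor any effect on the Week 16 comparison can be stated. The expectation that flares are commoner on placebo rests on the trial's own hypothesis. The conclusion assumes only that the class label means the same in sections 6.1 and 9.2.

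**What to change.** The sponsor's clinicians should reconcile sections 6.1 and 9.2 so that the rescue provision is consistent with entry on grounds of intolerance. How this is done, whether in the rescue paragraph, in a definition of intolerance or otherwise, is for them to decide.

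The reason for entry (intolerant or resistant) should be recorded at V1 if the eCRF does not already capture it. Rescue use, adverse events and withdrawals can then be described by entry reason, and the size of the issue can be seen in the data.

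The cost is one paragraph of protocol text and at most one eCRF field, with no added visits or procedures.

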#### 9.3. OPTIONAL SUB-STUDY

Patients included in the investigation center of Lyon, it will be proposed to participate to an optional pathophysiology sub-study to understand the mechanism of action of dupilumab.

For patients who give their written consent after receiving oral and written adequate information, a 3mm dorsal hand skin biopsy samples will be obtained at inclusion and repeated 16 weeks after the treatment initiation. The baseline biopsy will be performed at the most affected site of the dorsal hand. The 16-week biopsy will be performed close (2mm) to the baseline biopsy. Biopsy samples will be transferred to the lab unit (UDEAR Inserm U1056, Toulouse Purpan Hospital) and digested; cell suspensions will be sorted using flow cytometry. Sorted cell types will be exposed to a lysis buffer and RNA will be extracted. Single-cell RNA sequencing will be performed as described elsewhere (Define Major Fibroblast Populations in Human Skin Q18, Tabib T et al JID 2017) on each sample to identify distinct cell populations and distinct RNA signature within a specific cell type.

RNA-Sequencing will facilitate the ability to look at alternative gene spliced transcripts, post-transcriptional modifications, gene fusion, mutations/SNPs and changes in gene expression under treatment. Skin biopsy may lead to a located bleeding which will be avoided or limited by the cutaneous suture. A cutaneous infection may happen after performing a skin biopsy. The complete healing is usually obtained in 10 to 14 days. A permanent scar will persist. Smoking patients may experience healing difficulties. The clinical aspect of the scar varies from a person to an other. The healing issues which can arise are mainly delays of healing, hypertrophic scars, depressed scars, or change of skin color.

The pain associated to the biopsy sampling will be released according to the usual methods of pain management for example by a level 1 analgesic.

The stitches will be removed at Visit 2 by the site staff.

# DUPECZEMAIN RC31/18/0269 - Version $n^{\circ}$ 6.0

A biological collection will be realized with residual material after analysis (cutaneous biopsy, extracted ARN) to perform additional analyses (confirmation of a result for example) if needed. Biologic samples will be retained at UDEAR Inserm U1056, Toulouse Purpan Hospital.

Blood sample will be collected (10 ml) at V1 and V9. 1 heparin blood collection tube (5 ml) and 1 SST tube (5 ml).

Based on the results obtained from skin biopsies, the blood collection will allow us to check for pro- or antiinflammatory cytokines and neuropeptids in the serum and to perform transcriptomic Rnaseq analysis on circulating blood immune cells. These data will be complementary to those obtained from skin biopsy and should allow us to define a neuro-inflammatory signature in chronic hand eczema and to follow its evolution under treatment with dupilumab.

Blood samples will be identified and stored at the U1056 INSERM laboratory, UDEAR, Purpan Hospital, CHU de Toulouse ([name]).

